7.1.2. Method of Detecting AEs and SAEs

Care will be taken not to introduce bias when detecting AEs and/or SAEs. Open-ended and non-leading verbal questioning of the subject is the preferred method to inquire about AE occurrence. Appropriate questions include:

- "How are you feeling?"
- "Have you had any (other) medical problems since your last visit/contact?"
- "Have you taken any new medicines, other than those provided in this study, since your last visit/contact?"

7.1.3. Definition of Adverse Events

An AE is any untoward medical occurrence in a patient or clinical investigation subject, temporally associated with the use of a medicinal product, whether or not considered related to the medicinal product.

NOTE: An AE can therefore be any unfavorable and unintended sign (including an abnormal laboratory finding), symptom, or disease (new or exacerbated) temporally associated with the use of a medicinal product.

Events meeting the definition of an AE **include**:

- Any abnormal laboratory test results (haematology, clinical chemistry, or urinalysis) or other safety assessments (e.g., ECGs, radiological scans, vital signs measurements), including those that worsen from baseline, and felt to be clinically significant in the medical and scientific judgement of the investigator.
- Exacerbation of a chronic or intermittent pre-existing condition including either an increase in frequency and/or intensity of the condition.
- New conditions detected or diagnosed after study treatment administration even though it may have been present prior to the start of the study.
- Signs, symptoms, or the clinical sequelae of a suspected interaction.
- Signs, symptoms, or the clinical sequelae of a suspected overdose of either study treatment or a concomitant medication (overdose per se will not be reported as an AE/SAE unless this is an intentional overdose taken with possible suicidal/self-harming intent. This should be reported regardless of sequelae.).
- "Lack of efficacy" or "failure of expected pharmacological action" per se will not be reported as an AE or SAE. However, the signs and symptoms and/or clinical sequelae resulting from lack of efficacy will be reported if they fulfil the definition of an AE or SAE.

Events that **do not** meet the definition of an AE include:

- Any clinically significant abnormal laboratory findings or other abnormal safety assessments that are associated with the underlying disease, unless judged by the investigator to be more severe than expected for the subject's condition.
- The disease/disorder being studied, or expected progression, signs, or symptoms of the disease/disorder being studied, unless more severe than expected for the subject's condition.
- Medical or surgical procedure (e.g., endoscopy, appendectomy); the condition that leads to the procedure is an AE.

- Situations where an untoward medical occurrence did not occur (social and/or convenience admission to a hospital).
- Anticipated day-to-day fluctuations of pre-existing disease(s) or condition(s) present or detected at the start of the study that do not worsen.

7.1.4. Definition of Serious Adverse Events

If an event is not an AE per Section 7.1.3, then it cannot be an SAE even if serious conditions are met (e.g., hospitalization for signs/symptoms of the disease under study, death due to progression of disease, etc).

An SAE is any untoward medical occurrence that, at any dose:

- a. Results in death
- b. Is life-threatening

NOTE: The term 'life-threatening' in the definition of 'serious' refers to an event in which the subject was at risk of death at the time of the event. It does not refer to an event, which hypothetically might have caused death, if it were more severe.

c. Requires hospitalization or prolongation of existing hospitalization

NOTE: In general, hospitalization signifies that the subject has been detained (usually involving at least an overnight stay) at the hospital or emergency ward for observation and/or treatment that would not have been appropriate in the physician's office or out-patient setting. Complications that occur during hospitalization are AEs. If a complication prolongs hospitalization or fulfills any other serious criteria, the event is serious. When in doubt as to whether "hospitalization" occurred or was necessary, the AE should be considered serious.

Hospitalization for elective treatment of a pre-existing condition that did not worsen from baseline is not considered an AE.

d. Results in disability/incapacity, or

NOTE: The term disability means a substantial disruption of a person's ability to conduct normal life functions. This definition is not intended to include experiences of relatively minor medical significance such as uncomplicated headache, nausea, vomiting, diarrhea, influenza, and accidental trauma (e.g. sprained ankle) which may interfere or prevent everyday life functions but do not constitute a substantial disruption.

- e. Is a congenital anomaly/birth defect
- f. Medical or scientific judgment should be exercised in deciding whether reporting is appropriate in other situations, such as important medical events that may not be immediately life-threatening or result in death or hospitalization but may jeopardize the subject or may require medical or surgical intervention to prevent one of the other outcomes listed in the above definition. These should also be considered serious. Examples of such events are invasive or malignant cancers, intensive treatment in an emergency room or at home for allergic bronchospasm, blood

dyscrasias or convulsions that do not result in hospitalization, or development of drug dependency or drug abuse.

- g. Is associated with liver injury **and** impaired liver function defined as:
 - ALT \ge 3xULN and total bilirubin* \ge 2xULN (>35% direct), or
 - ALT \geq 3xULN and INR** > 1.5.

* Serum bilirubin fractionation should be performed if testing is available; if unavailable, measure urinary bilirubin via dipstick. If fractionation is unavailable and ALT \ge 3xULN and total bilirubin \ge 2xULN, then the event is still to be reported as an SAE.

** INR testing not required per protocol and the threshold value does not apply to subjects receiving anticoagulants. If INR measurement is obtained, the value is to be recorded on the SAE form.

• Refer to Appendix 1 for the required liver chemistry follow-up instructions.

7.1.5. Cardiovascular Events

Investigators will be required to fill out event specific data collection tools for the following AEs and SAEs:

- Myocardial infarction/unstable angina
- Congestive heart failure
- Arrhythmias
- Valvulopathy
- Pulmonary hypertension
- Cerebrovascular events/stroke and transient ischemic attack
- Peripheral arterial thrombosis
- Deep Venous Thrombosis
- Revascularization

This information should be recorded within one week of when the AE/SAE(s) are first reported.

7.1.6. Death Events

In addition, all deaths, whether or not they are considered SAEs, will require a specific death data collection tool to be completed. The death data collection tool includes questions regarding cardiovascular (including sudden cardiac death) and non-cardiovascular death.

This information should be recorded within one week of when the death is first reported.

7.1.7. Prompt Reporting of SAEs to GSK

Once the investigator determines that an event meets the protocol definition of an SAE, the SAE will be reported to GSK within 24 hours. Any follow-up information on a previously reported SAE will also be reported to GSK within 24 hours.

If the investigator does not have all information regarding an SAE, he/she will not wait to receive additional information before notifying GSK of the event and completing the appropriate data collection tool. The investigator will always provide an assessment of causality at the time of the initial report as described in Appendix 4.

7.1.8. Regulatory Reporting Requirements For SAEs

Prompt notification of SAEs by the investigator to GSK is essential so that legal obligations and ethical responsibilities towards the safety of subjects are met.

GSK has a legal responsibility to notify both the local regulatory authority and other regulatory agencies about the safety of a product under clinical investigation. GSK will comply with country specific regulatory requirements relating to safety reporting to regulatory authorities, IRBs/IECs and investigators.

Investigator safety reports are prepared for suspected unexpected serious adverse reactions according to local regulatory requirements and GSK policy and are forwarded to investigators as necessary. An investigator who receives an investigator safety report describing an SAE(s) or other specific safety information (e.g., summary or listing of SAEs) from GSK will file it with the IB and will notify the IRB/IEC, if appropriate according to local requirements.

8. DATA MANAGEMENT

For this study subject data will be entered into GSK defined electronic case report forms (eCRFs), transmitted electronically to GSK and combined with data provided from other sources in a validated data system.

Management of clinical data will be performed in accordance with applicable GSK standards and data cleaning procedures to ensure the integrity of the data, e.g., removing errors and inconsistencies in the data. Adverse events and concomitant medications terms will be coded using MedDRA (Medical Dictionary for Regulatory Activities) and an internal validated medication dictionary, GSKDrug. eCRFs (including queries and audit trails) will be retained by GSK, and copies will be sent to the investigator to maintain as the investigator copy. Subject initials will not be collected or transmitted to GSK according to GSK policy.

9. DATA ANALYSIS AND STATISTICAL CONSIDERATIONS

9.1. Hypotheses and Treatment Comparisons

The primary objective is to determine the safety and tolerability of single IV Doses of GSK2831781 in healthy volunteers and in patients with mild to moderate psoriasis.

There are no formal hypotheses planned.

An assessment of dose proportionality of AUC and Cmax, following single dosing, will be conducted separately for healthy volunteers and patients with psoriasis.

Where appropriate, an estimation approach will be used to address the study objectives where point estimates and corresponding confidence intervals will be constructed to provide a plausible range of values for the comparison of interest.

Exploratory comparisons will be conducted to investigate the effect of ADA status at baseline on the pharmacokinetics of GSK2831781.

9.2. Sample Size Considerations

The sample size is based on feasibility, and therefore there have been no formal sample size calculations

9.2.1. Sample Size Assumptions

[figure not shown]
The sample size is based on feasibility, and therefore there have been no formal sample size calculations conducted.

It is anticipated that sufficient number of healthy volunteers and patients will be enrolled in the study so that data are obtained from approximately 40 healthy subjects (26 on active, 14 on placebo) and approximately 27 psoriasis patients (18 on active, 9 on placebo).

Part A and Part B - Safety

The primary objective of the study is safety, where a number of safety events are of interest. A maximum of 6 subjects will receive each active dose and therefore if 0/6 of a particular safety event in the GSK2831781 group is observed, the upper limit of the exact 95% Confidence Interval (CI) indicates that a true incidence rate of 46.5% could not be ruled out. Whereas if 1/6 of the same safety event in the GSK2831781 group is observed, the upper limit of the exact 95% CI indicates that a true incidence rate of 62.9% could not be ruled out.

Using a Bayesian approach to determine the confidence interval around an observed safety event, we would assume a flat Beta (1,1) prior, and if we were to observe 1 safety event in 6 then the posterior distribution would be Beta (2, 6), as outlined below:

Where we can be 95% certain that the true probability of the safety event lies between 0.04 and 0.58.

Efficacy Assessment in Psoriasis Patients

The percentage change from baseline in PLSS in psoriasis patients can vary, with standard errors ranging from 6.9% to 11.1% (Boy *et al*, 2009). Assuming the greatest variability from this tofacitinib data and a sample size of 6 for each cohort, the 95% CI around the percentage change from baseline in PLSS point estimate would be plus or minus 26%, assuming a standard deviation of 24.8%.

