9.2.2. Sample Size Sensitivity

A sample size sensitivity analysis has been conducted on the primary endpoint, to investigate different safety event rates. If the number of subjects who completed each active dose is lower than 6, then the true incidence rates of safety events that could not be ruled out (as outlined in Section 9.2.1) would change. These changes are outlined in the table below:

N completing cohort	Number of particular a safety event observed with GSK2586184	Upper limit of exact 95% CI indicating that a true incidence rate of x% could not be ruled out
6	2 / 6	75.2%
6	3 / 6	84.9%
5	0 / 5	51.8%
5	1 / 5	69.1%
4	0 / 4	58.4%
4	1 / 4	76.4%
4	2 / 4	88.6%

N completing cohort	Number of particular a safety event observed with GSK2586184	Upper limit of exact 95% CI indicating that a true incidence rate of x% could not be ruled out
2	0 / 2	76.8%
2	1 / 2	93.4%

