5.1. Study Treatment & Sub-group Display Descriptors

	Treatment Group Descriptions					
	RandAll NG	Output	Output			
Code	Description	Treatment Label	Order			
A	0.0003mg/kg GSK2831781 IV single dose	0.0003mg/kg (ADA-ve)	2			
В	0.0015mg/kg GSK2831781 IV single dose	0.0015mg/kg (ADA-ve)	3			
С	0.0075mg/kg GSK2831781 IV single dose	0.0075mg/kg (ADA-ve)	4			
D	0.04mg/kg GSK2831781 IV single dose	0.04mg/kg (ADA-ve)	5			
Е	0.15mg/kg GSK2831781 IV single	0.15mg/kg (ADA-ve)	6			
	dose	0.15mg/kg (ADA+ve)	7			
		0.15mg/kg Combined	8			
F	0.5mg/kg GSK2831781 IV single dose	0.5mg/kg	10			
G	1.5mg/kg GSK2831781 IV single dose	1.5mg/kg	11			
Н	5mg/kg GSK2831781 IV single dose	5mg/kg	12			
P	Placebo IV single dose	Placebo for HV Combined	1			
		Placebo for PSO	9			

Notes:

- 1. ADA status as defined at screening
- 2. Combined treatment groups include subjects with ADA-ve and ADA+ve (only for healthy volunteers (HV))

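### The eleven upper limits labelled exact 95% CI in Protocol 9.2.1 and 9.2.2 are not exact 95% limits; ten lie below the two-sided Clopper-Pearson value

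*Protocol*

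**What the plan says.** Protocol 9.2.1 rests the sample size on feasibility and then describes precision for safety events. It starts from the statement that "A maximum of 6 subjects will receive each active dose". For 0/6, "the upper limit of the exact 95% Confidence Interval (CI) indicates that a true incidence rate of 46.5% could not be ruled out"; for 1/6, "the upper limit of the exact 95% CI indicates that a true incidence rate of 62.9% could not be ruled out". It then turns to a Bayesian interval, for which "we would assume a flat Beta (1,1) prior", and reports 0.04 to 0.58 for 1/6 from a Beta(2,6) posterior.

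The sensitivity table in 9.2.2 adds nine limits for n = 6, 5, 4 and 2 under the column header "Upper limit of exact 95% CI indicating that a true incidence rate of x% could not be ruled out". The neighbouring column header reads "Number of particular a safety event observed with GSK2586184".

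Section 9.2.1 also expects 26 healthy volunteers on active treatment. Table 1 in Protocol 3.1.2 assigns six active subjects to each of two 0.15 mg/kg cohorts. SAP 5.1 defines a combined 0.15 mg/kg display group with the note "Combined treatment groups include subjects with ADA-ve and ADA+ve".

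**The concern.** An exact 95% confidence limit for a binomial proportion normally means the two-sided Clopper-Pearson limit. The printed figures do not agree with it, and the sign of the difference is not constant, so rounding cannot explain them.

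This is a first-in-human study whose primary objective is safety and which plans no formal hypotheses. These limits are the protocol's only frequentist statement of what a cohort can exclude. A limit that is too low tells the reader that more has been ruled out than the data support. The wrong figures could also be copied into the study report.

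**Working it through.** **Inputs.** Event counts, denominators and stated limits come from Protocol 9.2.1 (0/6, 1/6) and the 9.2.2 table (the other nine). The flat prior Beta(1,1) comes from 9.2.1.

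**Formulas**, for x events in n:

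- Exact two-sided 95% upper limit: Beta⁻¹(0.975; x+1, n−x), the p at which P(X ≤ x) = 0.025.
- Exact one-sided 95% upper limit: Beta⁻¹(0.95; x+1, n−x).
- Flat-prior posterior percentile at level q: Beta⁻¹(q; x+1, n−x+1).

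**Reproducing the stated figures.** Only the last formula, with q = 0.9875, works.

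- 0/6: 1 − 0.0125^(1/7) = 0.4653, stated 46.5%.
- 1/6: solving (1−p)⁶(1+6p) = 0.0125 gives p = 0.6287, stated 62.9%.

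**The exact limits for the same two cases.**

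- 0/6: 1 − 0.025^(1/6) = 0.4593, so 45.9%.
- 1/6: solving (1−p)⁵(1+5p) = 0.025 gives p = 0.6412, so 64.1%. At the stated 62.9% the tail is 0.371⁵ × 4.145 = 0.0291, not 0.025.

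**All eleven (%):**

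| x/n | Stated | Flat prior, 98.75th percentile | Exact two-sided | Exact one-sided | Stated − exact two-sided |
|---|---|---|---|---|---|
| 0/6 | 46.5 | 46.53 | 45.93 | 39.30 | +0.6 |
| 1/6 | 62.9 | 62.87 | 64.12 | 58.18 | −1.2 |
| 2/6 | 75.2 | 75.17 | 77.72 | 72.87 | −2.5 |
| 3/6 | 84.9 | 84.86 | 88.19 | 84.68 | −3.3 |
| 0/5 | 51.8 | 51.83 | 52.18 | 45.07 | −0.4 |
| 1/5 | 69.1 | 69.13 | 71.64 | 65.74 | −2.5 |
| 0/4 | 58.4 | 58.37 | 60.24 | 52.71 | −1.8 |
| 1/4 | 76.4 | 76.44 | 80.59 | 75.14 | −4.2 |
| 2/4 | 88.6 | 88.57 | 93.24 | 90.24 | −4.6 |
| 0/2 | 76.8 | 76.79 | 84.19 | 77.64 | −7.4 |
| 1/2 | 93.4 | 93.40 | 98.74 | 97.47 | −5.3 |

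The flat-prior column matches eleven of eleven; neither exact column matches any. Blaker, mid-p, Jeffreys, Wilson (with and without continuity correction), Agresti-Coull and the flat-prior 97.5th percentile were also tried, and none reproduces the set. The worst case in tail terms is 1/2: at the stated 93.4%, the chance of one or fewer events is 1 − 0.934² = 12.8%, against the nominal 2.5%.

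**The Bayesian interval.** The 2.5th and 97.5th percentiles of Beta(2,6) are 0.037 and 0.579, which reproduces 0.04 to 0.58. So for 1/6 the section prints two upper limits, 62.9% and 0.58. Numerically they are the 98.75th and 97.5th percentiles of the same Beta(2,6), shown as two different methods.

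**Denominator.** From Table 1, active healthy volunteers number 1 + 1 + 6 + 6 + 6 + 6 = 26, as 9.2.1 says. A true maximum of six per dose would give 1 + 1 + 6 + 6 + 6 = 20. The 0.15 mg/kg dose therefore has 12 active subjects, and 0/12 gives an exact limit of 1 − 0.025^(1/12) = 26.5%.

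**The case against.** Four points can be made on the other side.

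*The direction depends on which exact method is meant.* The protocol names neither Clopper-Pearson nor sidedness. Against Blaker's exact two-sided limits (0/6 40.6%, 1/6 59.4%, 2/6 72.9%) or the one-sided limits, the stated values are too high in eight rows and too low only for 2/4, 0/2 and 1/2. This stands as a qualification: the count of ten holds against two-sided Clopper-Pearson, the usual reading of the label. It does not rescue the figures, because no exact method tried reproduces them.

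*How the figures were produced is inferred.* This also stands. The documents do not describe the calculation or explain a level of 0.9875. The mislabelling is established by the mismatch with the exact limits, whatever the origin.

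*Nothing depends on the figures.* True, and it limits the weight of the point. The sample size rests on feasibility, the stopping rules in Protocol 5.5 count events, and the safety analyses are descriptive. At n = 6 a reader concludes either way that six subjects rule out little.

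*The maximum of six is resolved elsewhere.* Table 1 and the cohort-based column in 9.2.2 do make the intent clear, and the combined 0.15 mg/kg group mixes ADA-negative DTH subjects with ADA-positive subjects without DTH. The sentence is still untrue as written, and the SAP reports the combined group.

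**Conclusion.** The point holds. All eleven limits are wrong for the method named. Taking the label to mean two-sided Clopper-Pearson, ten are too low by 0.4 to 7.4 points and one (0/6) is 0.6 points too high. At the planned n = 6 the errors are +0.6, −1.2, −2.5 and −3.3 points. The largest gaps fall at n = 4 and n = 2, which no cohort plans as its active number. The compound name in the 9.2.2 header and the per-dose maximum in 9.2.1 are also wrong as written. The consequence is a misstated description of precision for the primary objective, with no effect on design or conduct. The Beta(2,6) interval is correct and can stay.

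**What to change.** In Protocol 9.2.1 and 9.2.2:

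- Replace the eleven figures with the exact two-sided 95% limits and name the method as Clopper-Pearson: 0/6 45.9, 1/6 64.1, 2/6 77.7, 3/6 88.2, 0/5 52.2, 1/5 71.6, 0/4 60.2, 1/4 80.6, 2/4 93.2, 0/2 84.2, 1/2 98.7 (%).
- Change the compound in the table header to GSK2831781.
- State the maximum of six active subjects per cohort rather than per dose, and note that 0.15 mg/kg has 12 active subjects across cohorts 5 and 6 (0/12: 26.5%).
- Optionally add 0/1 (97.5%) for cohorts 1 and 2, which have one active subject each.

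This is a text correction. Sample size, stopping rules and planned analyses are unchanged. The only cost is that ten of the eleven figures become somewhat less favourable.

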9.2.2. Sample Size Sensitivity

A sample size sensitivity analysis has been conducted on the primary endpoint, to investigate different safety event rates. If the number of subjects who completed each active dose is lower than 6, then the true incidence rates of safety events that could not be ruled out (as outlined in Section 9.2.1) would change. These changes are outlined in the table below:

N completing cohort	Number of particular a safety event observed with GSK2586184	Upper limit of exact 95% CI indicating that a true incidence rate of x% could not be ruled out
6	2 / 6	75.2%
6	3 / 6	84.9%
5	0 / 5	51.8%
5	1 / 5	69.1%
4	0 / 4	58.4%
4	1 / 4	76.4%
4	2 / 4	88.6%

N completing cohort	Number of particular a safety event observed with GSK2586184	Upper limit of exact 95% CI indicating that a true incidence rate of x% could not be ruled out
2	0 / 2	76.8%
2	1 / 2	93.4%

9.2.3. Sample Size Re-estimation

No sample size re-estimation will be performed.

9.3. Data Analysis Considerations

Statistical analyses will be performed by, or under the auspices of, Clinical Statistics, QSci, GlaxoSmithKline.

Complete details of the planned statistical analyses will be provided in the Reporting and Analysis Plan (RAP).

9.3.1. Interim Analysis

Dependant on the dose cohorts reached in the escalation, formal interim analyses may be performed after the last subject in the Healthy Volunteer DTH cohort has completed their 4 week post dose assessment visit, and also after the last subject in the Psoriasis group has completed the final PK assessment visit, to inform internal development decisions. If required, additional interim analyses to contribute to internal development decisions may also be performed during Part B (psoriasis cohorts). Full details of interim analysis will be documented in a RAP addendum.

For Parts A and B of the study, review of safety, tolerability, available pharmacokinetic and DTH induration for healthy volunteers or PASI and PLSS for psoriasis patients will be performed by DEC to aid decisions to proceed to higher dose strengths or, between cohorts 5 and 6 to subjects with pre-existing ADA. This analysis can include review of individual subject data, summaries, graphical presentations and/or statistical analysis. Owing to the modest time intervals involved, all data to be used for dose escalation decisions will be preliminary, non-quality-controlled (non-QC'ed), data.

Safety/tolerability data monitoring and the decision to proceed to the next dose level of GSK2831781 will be made by the DEC (see Section 5.4 for more details).

The GSK Clinical Pharmacology Modeling and Simulation (CPMS) representative will extract PK data (including treatment information) from SMS2000 using unscrambled subject IDs. PK data will provide supporting evidence for each dose modification decision. Importantly, if the emerging PK data is significantly different from the predicted values, adjustment may have to be made to the planned doses (see Section 5.4). Dose modification decisions will take into account the emerging PK data, new PK prediction for the next dose and thus the expected safety cover for the next dose.

Standard Pharmacokinetic parameters will be derived for each subject by the GSK CPMS representative when possible. These parameters will be summarised by planned dose.

The criteria for switching from healthy volunteers to psoriasis patients are outlined in Section 3.2.1.

